following participant feedback accordingly. Standard unit costs will be used to cost resources. Responses to the EQ-5D-5L at baseline, 12 weeks and 12 months will be converted to utilities using the tariff recommended by NICE at the time of analysis.⁵⁸ We will use the area under the curve method to calculate QALYs.⁵⁹ To deal with missing data, we will explore the quantity of missing data and report on the missing rates for the different cost components and outcomes, by study group. We will also explore the nature of the missing data.

Since the relatively short time horizon of the trial will not capture the potential long-term health impact of the intervention, trial data will be incorporated into a long-term economic model with a lifetime horizon. We will conduct a literature review prior to designing the model to ensure we have the most up to date data on lifetime disease incidence, utilities and costs related to physical activity. The model is most likely to be a Markov state-transition model as these are particularly useful for modelling lifetime costs and health outcomes and have been used previously to assess the long-term cost-effectiveness of other physical activity interventions.⁶⁰⁻

⁶³

For both within trial and long term analyses we will perform deterministic sensitivity analysis to explore key assumptions and probabilistic sensitivity analysis (PSA)⁶⁴ to account for uncertainty arising from imprecision in the economic data. The PSA will generate bootstrapped replications of the incremental cost effectiveness ratio which will be plotted on the cost-effectiveness plane and used to construct a cost-effectiveness acceptability curve: this will depict the probability of the Walk with Me intervention being cost-effective compared to usual care at different willingness-to-pay per QALY thresholds. We will consider the performing subgroup analyses and this will be in keeping with the main statistical analyses. A detailed health economic analysis plan will be written in advance.

Methods for data collection

Outcome measures will be assessed at baseline, post-intervention (12 weeks from the start of the intervention in the intervention group or equivalent timing for the control group), 6 months (accelerometer only) and 12 months after baseline, in person, by a Research Assistant, who will be blind to group allocation.

Outcome measures will be collected at the participant's home, at a local community centre/venue, or their general practice if the participant would prefer. The meeting will adhere to COVID-19 public health and social measures that are in place at the time, such as wearing face coverings and physical distancing.

Participants will be asked to complete self-reported questionnaires (Appendices 15-25), with support from the Research Assistant if needed. When these are complete, resting blood pressure will be measured using an Omron M6 digital sphygmomanometer. In line with the American College of Sports Medicine guidelines, blood pressure will be recorded after the participant has been seated for at least five minutes, and measured twice, separated by at least one minute, and averaged.⁶⁵

Weight will be measured using a Seca weight scale and height measured using a portable stadiometer, and used to calculate body mass index. Waist circumference will be measured as the midpoint between the lowest rib and the iliac crest, using a fibre glass tape.

The SPPB includes three tests of balance and gait:

1) *Chair Rise Test*

For the chair stand test, whilst seated, the participant is asked to stand up and sit down as quickly as possible five times, without stopping. Whilst completing this, the participant should keep their arms folded across their chest. The movement will first be demonstrated by the Research Assistant. Timing, using a digital stopwatch, begins as soon as the participant bends forward at the hips, and ends when they sit back down after completing the fifth stand. The test is stopped if the participant starts to use their hands, or after one minute if they have not completed 5 rises, and if the Research Assistant is concerned about the participant's safety. If the test is stopped early, the time is recorded and the number of chair rises completed, along with the reason for stopping the test. If the participant is unable to complete 5 chair rises, they are given a score of 0 points. If they complete 5 chair rises in 16.70 seconds or more they score 1 point; in 13.70 to 16.69 seconds they score 2 points; in 11.20 to 13.69 seconds they score 3 points; and in 11.19 seconds or less they score 4 points.

2) *Standing Balance Test*

This test assesses the participant's ability to stand unaided for 10 seconds with their feet in three different positions. After demonstrating these positions (Figure 3), the participant is first asked to stand unsupported, feet together for 10 seconds. They are permitted to use their arms, bend their knees, or move their body to maintain their balance, but they will be asked to try to not move their feet. The research assistant stands next to the participant, allowing them to hold onto their arms to get their balance. Timing begins when the participant has their feet together and let's go of the supporting arm. If they can complete the 10 seconds, they progress to the semi-tandem stand. In the semi-tandem stand, the participant is asked to stand for up to 10 seconds with the heel of one foot placed by the big toe of the other foot. If they complete the semi-tandem stand, the participant completes the final balance test, the

full tandem stand. In this, one foot is placed directly in front of the other. The time balance is maintained for each test is recorded, to a maximum of 10 seconds. For each balance test not completed, a participant is given 0 points. If they hold the feet together and the semi-tandem balance for at least 10 seconds, they score 1 point each. If they hold the full tandem balance for at least 10 seconds, 2 points are awarded.

Figure 3: Feet Positions for Standing Balance Test

3) Usual walking speed

A distance of 3 metres is measured with a tape measure and a marker cone is placed at either end. The participant is asked to walk at their normal walking speed between the two cones and the time taken to complete the walk is recorded. The participant is allowed to use a walking aid if they normally use one when walking. The test is repeated twice and averaged. One point is awarded if the average time across the two tests is more than 6.52 seconds. Two points are awarded if the time is between 4.66 and 6.52 seconds; three points are awarded if the time is between 3.62 and 4.65 seconds, and four points are awarded if the time is <3.62 seconds.

At the end of the test period, participants will be fitted with an accelerometer and given an instructional guide on how to use it (Appendix 27) and a diary to record wear time (Appendix 28). They will be asked to wear the accelerometer during waking hours for 7 days. A pre-paid envelope will be provided to return the accelerometer to the study team.

In the case where COVID-19 public health and social measures make it impossible to meet face-to-face, a pack with outcome measures will be posted to participants in advance of an online video call or telephone call. This will include the accelerometer with instructions on how to fit and wear it, a measuring tape to measure waist circumference and self-completed measures. Participants will be asked to measure their weight using their own scales if they

have them and estimate their height. We will measure as many of the components of SPPB on the video call as is feasible.

Data management and statistical analysis

The primary analysis will be conducted on an intention-to-treat basis once primary outcome data collection is complete, with all randomised patients being analysed in the group to which they were allocated, regardless of the subsequent treatment they received at an a priori significance level of $p=0.05$ and reported in accordance with Consolidated Standards of Reporting Trials guidance.

The analysis will be undertaken by a statistician from the NICTU with no role in decision making about the ongoing conduct of the trial. We will describe baseline characteristics and follow-up measurements using suitable measures of central tendencies; means and medians with the associated standard deviations/interquartile ranges for continuous data; and frequencies and proportions for categorical data.

We will compare the primary outcome between groups adjusting for baseline within a generalized linear mixed model including mentor as a random effect to account for possible clustering. Similar methods will be used for other time-points and secondary outcomes. Exploratory analyses will be reported using 99% confidence intervals using interaction terms (treatment group by subgroup) for the subgroup of high and low household income to look at the moderating effect of individual level socio-economic position. We will also explore the moderating effect of gender, age, season and physical environment features on the results.

Process evaluation

A theory-driven process evaluation will be guided by the MRC Process Evaluation guidelines,⁶⁶ including an understanding of the impact of implementation, mechanisms of impact and context on the study outcomes.

Implementation

To assess implementation fidelity, we will assess an audio-recording of one randomly selected first meeting and a follow-up meeting for each peer mentor for content, delivery fidelity and the receipt and enactment of the intervention by participants, by comparing the content to the intervention manual (Appendix 10).⁶⁷ Audio-recordings will be made in a total of 70 participants sampled across different locations and a mixture of ages and sex. If the meetings are via online video call or telephone, they will be recorded with only the audio-file saved for fidelity

assessment. These will be analysed iteratively, and ongoing feedback given to peer mentors to enhance intervention fidelity, which will be carefully documented.⁶⁸

Intervention fidelity will also be assessed by asking all mentors and a sample of 35 participants (one from each peer mentor) to record a diary of the frequency and content of contacts (Appendix 29). Intervention fidelity will also be explored in the 12-week focus groups to explore perceptions of the delivery, receipt, and enactment of intervention components (e.g., BCTs such as monitoring progress). This information will be summarised at the end of the intervention.

Mechanisms of Impact

To assess the mechanism of any intervention effects (see logic model, Appendix 26), we will assess changes in physical activity self-regulation scale, physical activity and social activity self-efficacy and outcome expectancies using mediation analysis. Furthermore, the use of BCTs by participants will be assessed in focus groups, and the delivery of BCTs by peer mentors will be assessed using a coding framework from included BCTs in audio-recordings described above.

Any adaptations and modifications to the intervention will be recorded using the FRAME methodology to capture adaptations or modifications made by the peer mentors or participants, and those resulting from changes in COVID-19 public health or social measures (Appendix 30).⁶⁹

Contextual factors

Contextual factors⁶⁶ that may influence the implementation and variation in outcomes, such as participant characteristics and physical environment features that may impact on walking will be explored in the post-intervention focus groups with participants and mentors.

Based on previous research,⁷⁰ these will include the impact of feelings of safety while walking; access to recreational facilities, parks/public open space and shops; greenery and aesthetically pleasing scenery; walk-friendly infrastructure; and access to public transport. To prompt discussion, we will present each focus group participant with a screen shot from the WalkScore (<https://www.walkscore.com>) output for their local neighbourhood. WalkScore is freely available tool that reports walkability within a 30-minute walk from a person's house. The score is a measure of pedestrian friendliness and the number of amenities in the neighbourhood, measured on a scale of 0 to 100. As well as the score, a map is available,

highlighting a variety of local amenities such as parks and shops as well as roads. This will prompt individuals to describe where they walk and what barriers and facilitators to walking they may encounter in their locality.

In addition, we will assess the moderating effect of the physical environment on the results, using WalkScore as a proxy for neighbourhood walkability and area level data on crime and the living environment using relevant indicators from the Northern Ireland Multiple Deprivation Measure (<https://www.nisra.gov.uk/statistics/deprivation/northern-ireland-multiple-deprivation-measure-2017-nimdm2017>).

At 12 weeks and 6 months, we will invite a purposeful sample of 30 intervention group participants to a focus group. A mixture of males and females and different age groups will be invited. We will run between four and six focus groups depending on participants' availability and location. We will also invite their mentors to one of four separate focus groups. They will be provided with a Peer Mentor Participant Information Sheet (v1: 6th November 2021; Appendix 11). Individuals who agree to participate will be asked to provide written consent (v1: 6th November 2021; Appendix 12).

The aim of these focus groups will be to: (1) understand the experience of participants and mentors; (2) explore if SCT and the logic model describe the experience of participants; (3) explore the barriers and facilitators to longer term maintenance of activity; (4) explore the intervention BCTs used as part of making the initial changes in physical activity and to maintain activity at six months. Anonymity and confidentiality for reporting will be ensured. Topic guides (Appendix 31) will facilitate discussions. Audio recordings of focus groups will be transcribed and uploaded into QSR NVivo (v12) along with field notes. Analysis will explore the logic model, guided by the five stages of the Framework approach:⁷¹ familiarisation; identifying a thematic framework; indexing; charting; mapping and interpretation.

Assessment of unanticipated outcomes

This is a low risk intervention, and we do not anticipate any serious adverse events. Adverse event reporting will follow the Health Research Authority guidelines on safety reporting in non-clinical trial investigational medicinal product studies (CTIMPs). Participants will be encouraged to report adverse events (e.g. musculoskeletal problems or falls) to the study team. Adverse events reported by participants will be recorded on a standard proforma (Appendix 32).⁷²

Serious adverse events, defined as an unexpected occurrence resulting in death, threat to life or hospitalisation or otherwise considered medically significant by the investigators will be recorded and assessed by clinical members of the study team who are not directly involved in the day-to-day running of the trial for causality and expectedness, using the definitions provided in Table 3.

Table 3: Serious Adverse Event (SAE) causality definitions	
Causality assessment	Description
Unrelated	There is no evidence of or rationale for any causal relationship.
Likely to be related	There is evidence, and a rationale, to suggest a causal relationship and other possible contributing factors can be ruled out.

If, in the opinion of the clinical co-investigator, an SAE occurring to a research participant is classified as related to the intervention, then the Chief Investigator will be responsible for reporting it to the Sponsor and to the research ethics committee which issued the favourable ethical opinion, using the SAE report for non-CTIMPs (published on the Health Research Authority website) within 15 days of becoming aware of the event.

Dissemination of Findings

We will target programme commissioners, general public and primary care clinicians with targeted outputs, using plain English summaries to ensure all resources are accessible to a wide audience. We will produce a range of outputs for different audiences, including a study website with regular updates, newsletters for participants, stakeholders and policy makers, lay summaries of evidence, peer reviewed publications and conference presentations at national and international conferences. We will prepare papers for publication in the public health literature.

To disseminate the ongoing progress of the study, and the study findings to members of the public and the wider public health community, we will distribute lay summaries of evidence and circulate these via social media channels (Twitter, Facebook). We will also seek three intervention participants to volunteer to keep a regular vlog of their experience of the programme. They will be asked to record a short 30 second video on their mobile phone, describing their experience as they progress through the intervention and to reflect on the process and what they have learnt. These will be collated and shared via Youtube and social media, with the participants' permission (Appendix 33).

Project Timelines

This project will last for 36 months. It is anticipated that all participants will be recruited between April 2022 and March 2023. This will allow for post-intervention assessments to take place between July 2022 and June 2023, 6-month assessments to take place between October 2022 and September 2023, and 12 month assessments between April 2023 and March 2024, leaving nine months for analysis, write-up and dissemination.

References

1. United Nations. World Population Ageing 2017 Highlights. New York: United Nations; 2019.
2. Piercy KL et al. The Physical Activity Guidelines for Americans. *Jama* 2018;320(19):2020-28.
3. Department of Health and Social Care. UK Chief Medical Officers' Physical Activity Guidelines. London: Department of Health and Social Care; 2019.
4. Cunningham C. Consequences of physical inactivity in older adults: A systematic review of reviews and meta-analyses. *Scand J Med Sci Sports*. 2020;30(5):816-827.

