This Walk with Me study is a two-arm parallel-group randomised trial involving 348 older adults aged 60 years or over living in socio-economically disadvantaged communities. Individuals will be randomised to either a 12-week peer-led walking intervention group or a minimal intervention control group. Baseline measures will be collected before randomisation, at 12 weeks (post-intervention), six months (accelerometer only) and 12 months. An internal pilot will be included with pre-specified stop-go criteria. The independent Trial Steering Committee (TSC) will assess the feasibility of progressing past the first 6-month internal pilot period based on the recruitment rates of peer mentors and participants. Using a 'traffic light' system previously recommended,¹⁹ progression will be based on the percentage of the target sample achieved half way through the recruitment period (6-months): (a) proceed: $\geq 50\%$ of the total sample of peer mentors and participants recruited; (b) modify: 25-49% of the total sample of peer mentors and participants recruited; or stop: $< 25\%$ of the total sample of peer mentors and participants recruited. After six months, any required changes in the recruitment strategy and/or introduction of new recruitment pathways will be agreed with the TSC and the funder. The participants recruited in the pilot study will be included in the overall analysis. Qualitative data will also be collected at 12 weeks and six months. Process and economic evaluations will be nested within the trial.

Setting and Participants

The study will target community-dwelling older adults, aged 60 years or over living in areas of socio-economic disadvantage, defined as most disadvantaged quartile of electoral wards in NI, based on the NI Multiple Deprivation Measure (NIMDM) (www.nisra.gov.uk), which covers a large geographical area.

Recruitment

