A mixture of recruitment strategies will be used. To identify potentially eligible participants for postal receipt of study information and an invitation to participate from their general practice, 12 practices will be invited to collaborate. The recruitment of these practices, based in target communities, will be conducted by the NI Clinical Research Network (Primary Care). Staff in collaborating practices will be asked to identify potential participants. This could be achieved by practice staff through a computerised search of patient records for individuals aged 60 years or over, or the identification of known individuals who would be eligible to participate. The practice will send a letter (Appendix 1) to potential participants on practice headed paper and an invitation to contact the study team if they wish to participate, using an enclosed reply slip (Appendix 2) and a stamped addressed envelope. As in the pilot study,¹⁸ practices will

receive a payment of £50 per recruited participant in recognition of the additional work for practice staff that recruitment involves.

We will also disseminate information (Appendix 3) about the study through community organisations and centres, libraries, faith based groups and churches; and the email lists and social media outlets of project partners. In addition, to boost the recruitment of men, we will also specifically target existing men's groups (such as men's sheds, Men's Health Forums, Farmer's Unions, and sporting organisations such as the Irish Football Association, Ulster Rugby and the Ulster Gaelic Athletic Association). Individuals who wish to participate will be asked to contact the study team by telephone, in writing by returning an opt-in card, or by email.

Screening

Following initial contact with the study team, interested individuals will be screened for eligibility over the telephone by a trained researcher, following the Participant Eligibility Form (Appendix 4). Reasons for exclusion and the route of recruitment will be recorded.

Eligibility Criteria

The inclusion criteria are:

- Living in socio-economically disadvantaged community, defined as most disadvantaged quartile of electoral wards in NI according to the NIMDM.

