- Unable to communicate in English

Informed consent

The flow of participants through the study is described in Figure 1. Individuals deemed eligible to participate will be posted / given a study pack containing an information sheet (v1: 6th November 2021; Appendix 5) and consent form (v1: 6th November 2021; Appendix 6) along with a stamped addressed envelope. The information sheet will contain the contact details of the research team should the individual have any further questions they wish to ask. Individuals who agree to participate will be asked to provide the project manager with written informed consent following at least a 24 hour cooling off period to allow them to consider participating. They will be given a duplicate of the consent form which will also contain the details of the researcher should they wish to ask any further questions about the study. With participant's permission, a letter will be sent to their GP to inform them of their participation (Appendix 7).

Figure 1: Study flowchart for the Walk with Me RCT

Randomisation

A statistician from the Northern Ireland Clinical Trials Unit (NICTU) will generate the randomisation sequence using a computer program and randomly permuted block randomisation with mixed block sizes. After written consent to participate is received and baseline outcomes measures have been collected, participants will be randomised to the intervention or the control group. The Research Project Manager will phone the NICTU and provide confirmation of the participant's consent, eligibility and participant ID number. The NICTU will provide the Research Project Manager with the participant's group allocation.

Sample Size

Based on the findings from our pilot study,¹⁸ and recent systematic reviews,²⁵⁻²⁶ a sample size of 133 in each group will have 90% power to detect an effect size of 0.4 based on a two group t-test. This is equivalent to an increase of approximately 50 minutes/week of MVPA in the intervention group compared to the control group. A previous trial of a walking intervention in older adults has demonstrated that this would be a clinically significant change in terms of a reduction in the risk of fatal and nonfatal cardiovascular events, reduction in the risk of fractures and reductions in systolic and diastolic blood pressure.²⁷

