Individuals allocated to the control group will be contacted by a health improvement officer based at the Institute for Public Health. They will be thanked for their participation and informed that they will be contacted at 12 weeks, 6 months and 12 months for follow-up assessments. They will be given a copy of the Public Health Agency's information booklets on active ageing (Appendix 13) and healthy eating (Appendix 14). They will not receive any additional physical activity support over the course of the research study. To encourage retention, they will be contacted again by a health improvement officer at nine months to confirm contact details. Participants in the intervention group will be contacted at the same time to encourage retention. After the final data collection point, they will be given the opportunity to discuss with a member of the research team the availability of local physical activity opportunities (e.g. local walking groups). In line with approaches used in our pilot study¹⁸ and other interventions in older adults,¹³ they will also be offered a pedometer and physical activity diary during this meeting.

Outcome Measures

Demographic and outcome measures will be measured across four time points, as presented in Table 2.

Table 2: Outcome assessment according to the Walk with Me logic model and pilot study.

Data Collection	Baseline	3M	6M	12M
Socio-demographic: age, sex, marital status, car ownership (Appendix 15)	✓			
Actigraph accelerometer	✓	✓	✓	✓
Anthropometry – weight, body mass index (BMI), waist circumference	✓	✓		✓
Resting blood pressure	✓	✓		✓
Short physical performance battery (SPPB) ⁴⁰	✓	✓		✓
Warwick-Edinburgh Mental Well-Being Scale (WEMWBS) ⁴¹⁻⁴² (Appendix 16)	✓	✓		✓
EQ-5D-5L questionnaire ⁴³ (Appendix 17)	✓	✓		✓

UCLA Loneliness Scale ⁴⁴ (Appendix 18) and the Lubben Social Network Scale ⁴⁵ (Appendix 19)	✓	✓		✓
Physical activity self-regulation scale ⁴⁶ (Appendix 20)	✓	✓		✓
Physical activity and social activity self-efficacy ⁴⁷ (Appendix 21)	✓	✓		✓
Physical activity and social activity outcome expectancy ⁴⁸ (Appendix 22)	✓	✓		✓
Service use questionnaire (Appendices 23-25)	✓	✓		✓
Unintended consequences or adverse events		✓		✓

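### Individual randomisation without a household rule lets cohabiting partners fall into opposite arms, which would dilute the primary MVPA difference

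*Protocol*

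**What the plan says.** **Unit of allocation.** Under Study Design, "Individuals will be randomised to either a 12-week peer-led walking intervention group or a minimal intervention control group". The Randomisation section specifies "randomly permuted block randomisation with mixed block sizes" and says that, once consent and baseline measures are in hand, "participants will be randomised to the intervention or the control group". It has the project manager telephone the trials unit to "provide confirmation of the participant's consent, eligibility and participant ID number". No household information is passed on.

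**Who can enter.** Under Recruitment, practices may identify people through "a computerised search of patient records for individuals aged 60 years or over", or staff may name people they know to be eligible. Community organisations, churches, libraries and men's groups are also approached. The Eligibility Criteria admit both sexes from age 60 with no upper limit, and neither list limits entry to one person per household.

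**What controls get.** They receive information booklets. The Control group section adds: "They will not receive any additional physical activity support over the course of the research study".

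**Clustering.** The Sample Size section inflates for mentor clustering only. The model under Data management and statistical analysis is described as "including mentor as a random effect to account for possible clustering". The protocol does not discuss contamination between arms.

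**The concern.** Recruitment is local: 12 practices in target communities, plus neighbourhood groups. Two people at one address can both be invited, both opt in and both meet every listed criterion. The trials unit would have no means of recognising them as a pair, so they may be allocated to different arms.

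The intervention is easily shared at home. It consists of a pedometer with daily step goals, a written action plan, walking, attendance at a local activity group, and pedometer logs with monthly calls to month six. It is built on social support. A control whose partner is doing all this may become more active too, and the between-group difference in MVPA would then understate the effect of the programme. The analysis plan cannot recover this once people are allocated, so the matter belongs in the protocol.

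**Working it through.** **Step 1: reproduce the protocol's sample size.** Inputs from the Sample Size section are effect size 0.4, 90% power, ICC 0.01, 5 participants per mentor and 20% dropout. The significance level of 0.05, read as two-sided, comes from the analysis section.
- A two-sample t-test needs 132.3 per group, rounded up to 133.
- Design effect: 1 + (5 − 1) × 0.01 = 1.04. Then 133 × 1.04 = 138.3, rounded up to 139.
- Dropout: 139 / 0.8 = 173.75, rounded up to 174 per group, or 348 in total.

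All the stated figures reproduce. The effective number per group is 139 / 1.04 = 133.65, which gives 90.3% power. Since 0.4 is equated with about 50 min/week, the implied SD is 50 / 0.4 = 125 min/week.

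**Step 2: how many controls would be exposed.** Let s be the share of participants enrolled as couples. The documents do not give it, so 10%, 20% and 30% are assumed. Under independent 1:1 allocation half the couples are split, so the exposed share of controls is f = s / 2, that is 5%, 10% or 15%. This is slightly low. Two partners who fall in the same permuted block are split more often: with probability 2/3 in a block of four and 3/5 in a block of six (illustrative sizes; the protocol states none).

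**Step 3: dilution.** Let c be the share of the effect taken up by an exposed control, also assumed. The diluted effect size is d = 0.4 × (1 − f × c). For example, s = 20% and c = 0.5 give 0.4 × (1 − 0.10 × 0.5) = 0.38, or 0.38 × 125 = 47.5 min/week.

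| Share in couples | Uptake | Effect size | min/week | Power |
|---|---|---|---|---|
| 0% | – | 0.400 | 50.0 | 90.3% |
| 10% | half | 0.390 | 48.8 | 88.8% |
| 20% | half | 0.380 | 47.5 | 87.2% |
| 30% | half | 0.370 | 46.3 | 85.4% |
| 10% | full | 0.380 | 47.5 | 87.2% |
| 20% | full | 0.360 | 45.0 | 83.5% |
| 30% | full | 0.340 | 42.5 | 79.1% |

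Restoring 90% power by enlarging the trial would need about 366 to 478 participants in total across the six contaminated scenarios.

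**Step 4: are the standard errors affected?** Couples in the same arm add covariance to the difference in means, and split couples remove the same amount. With half of each, the two cancel. Simulation of 278 analysed participants (2 × 139), with 30% in couples, an assumed within-couple ICC of 0.5 and no household term, gave a true SD of the difference and a mean estimated SE that were both 0.120 to three decimals. Type I error was about 5%.

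**Step 5: cost of allocating couples as units.** Here the cancellation is lost, and the design effect is about 1 + s × household ICC. At s = 30% and ICC 0.5 this is 1 + 0.3 × 0.5 = 1.15. The effective number per group is then 133.65 / 1.15 = 116.2 and power is about 86%. For s from 10% to 30% and ICC from 0.1 to 0.5, holding the design power needs about 350 to 400 in total.

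**The case against.** The strongest case against is that individual randomisation is a legitimate choice and that every figure for the size of the problem is assumed. Both partners would have to opt in and pass the screens for inactivity, cognition, frailty, medical readiness and return to work, so couples may be few. A control spouse gets no mentor meetings, no personal goals and no calls, so full uptake is implausible. These points stand, and full uptake is offered only as an upper bound.

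The planned model also adjusts for baseline, which the t-test ignores. If 0.4 is on the outcome scale and the baseline correlation is 0.5 (both assumptions), power is 96% without contamination, 95% with 20% in couples and half uptake, and 89% with 30% and full uptake. At a correlation of 0.3 the figures are 93%, 90% and 83%. This may cushion the loss of power, but it does not remove the bias towards zero.

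The remedy has a price as well. Allocating couples together inflates the variance and, if done carelessly, reveals a later-joining partner's arm before consent and baseline. That stands and shapes the fix. The Participant Eligibility Form (Appendix 4) and the flowchart are not shown, so an operational household question cannot be excluded. The listed criteria contain none.

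Three stronger readings are tempting but not supported:
- A reader might infer that the mentor-only model gives standard errors that are too small. Under individual randomisation it does not, because same-arm and split couples cancel.
- A reader might infer that letters go to everyone aged 60 or over. The age search is one of two options.
- A reader might take the Control group section as forbidding any activity influence on controls. It describes what the study supplies, not what a partner may share.

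**Conclusion.** The point holds as a risk of dilution. Nothing in the protocol stops cohabiting partners from being split across arms, and any carry-over would bias the primary MVPA difference towards zero. On the protocol's own t-test basis, with 10% to 30% of participants in couples, power falls from 90.3% to between 88.8% and 85.4% at half uptake, and to between 87.2% and 79.1% at full uptake. The contrast shrinks from 50 min/week to between 48.8 and 42.5 over the whole range.

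The share of couples and the carry-over are assumptions, so this is not a demonstrated bias, and the effect is small if few couples enrol. The sample size arithmetic is correct, and the validity of the standard errors is not in question. It is worth acting on because prevention is cheap and allocation cannot be reversed.

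**What to change.** Ask at telephone screening whether anyone in the household is taking part or has applied, and record a household identifier. Then state one of two rules in the Eligibility Criteria or Randomisation section:

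1. **One participant per household.** The total stays at 348 and the model is unchanged. The cost is a few lost recruits, which matters a little because progression from the internal pilot depends on recruitment.
2. **Joint allocation.** Allocate cohabiting participants as a unit, but only after both have consented and completed baseline, so that concealment is kept. Pass the household identifier to the trials unit and add a household term to the model. The cost is the small variance inflation in Step 5. The rule must also say what happens when a partner asks to join after the first has been allocated; not enrolling that person would preserve concealment.

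Either rule needs one screening question and one instruction to the randomisation service. For anyone already allocated, the identifier at least lets the report state how many split couples there were.
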